4. PARTICIPANT ENTRY

4.1. PRE-REGISTRATION EVALUATIONS

As participants will be those invited as part of the NHSBSP, no additional pre-registration evaluations will be required.

4.2. INCLUSION CRITERIA

The inclusion criteria will match those used by the NHSBSP, as all invitations will come directly from the programme, as per usual care. These include:

- Aged between 50 to 70 at the time of invitation
- Lives within London screening region
- Registered as female with GP

4.3. EXCLUSION CRITERIA

The exclusion criteria will match those used by the NHSBSP, as all invitations will come directly from the programme, as per usual care. These include:

- Previous attendance at breast screening in the current (3-year cycle)
- Opted out of receiving SMS messages
- Opted out of screening
- Previous bilateral mastectomy

4.4. WITHDRAWAL CRITERIA

As messages will be sent through the NHSBSP and undertaken as part of the usual care process the withdrawal criteria will match those of the screening service. Individuals can opt-out of both messaging or screening at any time throughout the process and will be excluded. No data for those who highlight opt-outs will be held or analysed by researchers. The opt-out decision will be retained by screening services, and they will not be contacted with the messages. This process involves either indicating opt-out through the national data opt-out (should they wish not for their data to be used) or by contacting the London breast cancer screening service using the details provided on their invitation letter. Those who have opted out will not have data passed to researchers for analysis. However, following pseudo-anonymisation it will not be possible for researchers to identify individuals who wish to have their data withdrawn.

5. ADVERSE EVENTS

5.1. DEFINITIONS

Adverse Event (AE): any untoward medical occurrence in a patient or clinical study subject.

Serious Adverse Event (SAE): any untoward medical occurrence or effect that:

- **Results in death**
- **Is life-threatening** – refers to an event in which the subject was at risk of death at the time of the event; it does not refer to an event which hypothetically might have caused death if it were more severe
- **Requires hospitalisation, or prolongation of existing inpatients' hospitalisation**
- **Results in persistent or significant disability or incapacity**
- **Is a congenital anomaly or birth defect**

Medical judgement should be exercised in deciding whether an AE is serious in other situations. Important AEs that are not immediately life-threatening or do not result in death or hospitalisation but may jeopardise the subject or may require intervention to prevent one of the other outcomes listed in the definition above, should also be considered serious.

5.2. REPORTING PROCEDURES

All adverse events should be reported. Depending on the nature of the event the reporting procedures below should be followed. Any questions concerning adverse event reporting should be directed to the Chief Investigator in the first instance.

5.3.1 Non serious AEs

All such events, whether expected or not, should be recorded- it should be specified if only some non-serious AEs will be recorded, any reporting should be consistent with the purpose of the trial end points.

5.3.2 Serious AEs

An SAE form should be completed and emailed to the Chief Investigator within 24 hours. However, relapse and death due to breast cancer, and hospitalisations for elective treatment of a pre-existing condition do not need reporting as SAEs.

All SAEs should be reported to the <name of REC> where in the opinion of the Chief Investigator, the event was:

- 'related', ie resulted from the administration of any of the research procedures; and
- 'unexpected', ie an event that is not listed in the protocol as an expected occurrence

Reports of related and unexpected SAEs should be submitted within 15 days of the Chief Investigator becoming aware of the event, using the NRES SAE form for non-IMP studies. The Chief Investigator must also notify the Sponsor of all related and unexpected SAEs.

Local investigators should report any SAEs as required by their Local Research Ethics Committee, Sponsor and/or Research & Development Office.

Contact details for reporting SAEs

[contact]

CI email (and contact details below)

Fax: xxx, attention xxx

Please send SAE forms to: xxx

Tel: xxx (Mon to Fri 09.00 – 17.00)

6. ASSESSMENT AND FOLLOW-UP

The end of the study will be 6 months after initiation. Following this period, we will undertake an assessment of the uptake of screening by participants. At two time-points (during and at the end of the study period) feedback from participants who have watched the video will be sought. This will involve anonymised feedback regarding an individual's opinions on the content, characters, and style of the video. This feedback will be hosted on the video website and will be optional. Informed consent will be sought for the completion of this anonymous

[figure not shown]
questionnaire. The questionnaire is available at this link:
https://imperial.eu.qualtrics.com/jfe/form/SV_1YPMnU1vvyeNDxA

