4.3. EXCLUSION CRITERIA	9
4.4. WITHDRAWAL CRITERIA	9
5. ADVERSE EVENTS	9
5.1. DEFINITIONS	9
5.2. REPORTING PROCEDURES	10
6. ASSESSMENT AND FOLLOW-UP	10
7. STATISTICS AND DATA ANALYSIS	11
8. REGULATORY ISSUES	12
8.1. ETHICS APPROVAL	12
8.2. CONSENT	12
8.3. CONFIDENTIALITY	12
8.4. INDEMNITY	13
8.5. SPONSOR	13
8.6. FUNDING	13
8.7. AUDITS	13
9. STUDY MANAGEMENT	13
10. PUBLICATION POLICY	13
11. REFERENCES	13

GLOSSARY OF ABBREVIATIONS

BCT	Behavioural Change Technique
ICL	Imperial College London
NHS	National Health Service
NHSBSP	NHS Breast Screening Programme

NHSE	NHS England
RCT	Randomised Controlled Trial
SMS	Short Message Service

KEYWORDS

Breast cancer screening, uptake, behavioural science, SMS messaging

STUDY SUMMARY

TITLE Investigating the use of behavioural science informed messages to facilitate attendance at Breast Cancer Screening

DESIGN Randomised Controlled Trial

AIMS To determine the impact of SMS messages, and a video developed using behavioural science upon the uptake

[figure not shown]
OUTCOME MEASURES Primary: percentage uptake of the invitation to screen. Secondary: percentage uptake of the invitation to screen amongst population subgroups (e.g. by demographic factors, and by invitation type).

POPULATION All women aged between 50 and 70, invited to screen in the London breast cancer screening region.

ELIGIBILITY Eligible to attend the NHSBSP in London during the study period.

DURATION 6 months

REFERENCE DIAGRAM

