3. STUDY DESIGN

This study will be conducted as a randomised control trial (RCT) in the London screening region of the NHSBSP. The study will last over 6 months. The administrative hub for the NHSBSP in London is based at the Royal Free Hospital, who will oversee invitation scheduling, message delivery and outcome data collation through their existing delivery systems.

Participants will be randomised using simple randomisation method in a 1:1:1 fashion to either intervention arm or usual care. Randomisation will utilise a computerised system in which each participant who is due for screening in the study period is randomly allocated a

number corresponding to the message they will receive. This will be undertaken by the screening hub, and will be passed on to the message delivery service who will ensure the correct template is sent.

Written invitations are sent, as standard practice, by the NHSBSP to invite women to either (1) an appointment at a set time, date and location (so-called timed invitations) or (2) to call and book an appointment (or open invitation). Following this, as part of usual care, those selected for open invitations will receive a first SMS 7 days post written invitation. They will then receive two SMS reminders, 7 days and 2 days prior to the appointment, once it has been booked. Those who receive timed invitations will just receive the two reminder messages, 7 and 2 days prior to the appointment. The decision to offer an individual a timed or open invitation is made by the screening service based on their covid-19 recovery process, and will not be altered by this project.

This RCT will involve randomising participants to receive the usual care messages (according to the timings outlined above), a plain text SMS incorporating BCTs or the BCT SMS with a new link to a video incorporating more BCTs (see **figure 1 for message content in each of the three trial arms**).

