The content of the intervention messages, and the video have been developed through extensive Patient and Public Involvement and Engagement work including 10 interviews, 2 focus groups and 2 co-design workshops. Members of the public have been consulted throughout the process, especially regarding the representations of individuals in the video, and the message content. The feedback received has been used to alter the materials, and further feedback received. Through this iterative approach we have ensured content is appropriate. We have also sought feedback from members of the Oremi centre (a mental health day service specifically for African Caribbean and Arabic Speaking adults) and Gendered Intelligence (a trans-led organisation to improve the quality of life of trans people) to ensure individuals from these groups are happy with representations. Screening commissioners, led by [name] (NHS England Breast Screening Lead, London), have also approved this content. The NHS Identity team have provided approvals for the use of NHS logos/branding, and the team at London Northwest Healthcare NHS Trust approved the use of their name.

The video will be hosted on a private page on the Imperial College London website, which will be available only to those who have been sent the link. The video will be translated into several languages, with voice overs also available in different languages, to ensure people from a diverse background are able to understand the content.

After 3 months from the initial written invitations, data will be collated from the breast screening hub regarding whether an individual attended an appointment and whether the messages were successfully sent. This will be repeated at 6 months corresponding to the key performance indicator of the service.

Figure 1. Message content for timed and open invitations for the trial arms (a) control, (b) plain text SMS with BCTs and (c) BCT SMS with new link to BCT video.

Reminders at 7 and 2 days prior to appointment		
a) Control	b) Behavioural SMS	c) Behavioural SMS + Video

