3.1. STUDY OUTCOME MEASURES

The primary outcome of this study is the percentage uptake of breast cancer screening, three months after the initial invitation letter. This will be reported as both intention-to-treat and per protocol, according to whether the SMS messages were received. Currently it is estimated that the screening service has access to 80% of mobile numbers of invitees.

Secondary outcomes will involve how the uptake differs according to:

- demographics (e.g. ethnicity, deprivation)
- invitation type (open and timed invitation)
- attendance history (previous non-attendee, recurrent attendee, first-time invitee)

We will also repeat the primary analysis to determine the uptake at 6 months. These timepoints were chosen firstly from the literature which suggests the impact of behavioural interventions occurs in the acute decision phase, but also following discussion with the screening service where 6 monthly reporting coincides with a key performance indicator.

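### The six-month end of study does not reconcile with randomisation throughout that period and uptake measured three and six months after each invitation letter

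*Combined protocol and SAP*

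**What the plan says.** **Length of the study.** The study summary gives "DURATION 6 months". Section 3 says "The study will last over 6 months", and section 6 says "The end of the study will be 6 months after initiation".

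**Who enters, and when.** Section 3 has a computerised system in which "each participant who is due for screening in the study period is randomly allocated" a number for the message to be sent. The summary ties eligibility to the same span: "Eligible to attend the NHSBSP in London during the study period".

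**When the outcome is measured.** Section 3.1: "The primary outcome of this study is the percentage uptake of breast cancer screening, three months after the initial invitation letter". The same section repeats the primary analysis for uptake at 6 months. On data collection, section 3 says "After 3 months from the initial written invitations, data will be collated from the breast screening hub", with a repeat at 6 months that matches the screening service's performance indicator.

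**When uptake is assessed.** Straight after fixing the end of study, section 6 adds: "Following this period, we will undertake an assessment of the uptake of screening by participants".

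No section gives a date for the last invitation letter, an invitation window separate from follow-up, a date for either data extraction, or a rule for women whose follow-up is incomplete.

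**The concern.** One six-month period is asked to hold both the invitations and the follow-up. If women are randomised as they fall due throughout it, anyone invited in its second half reaches three months after the stated end. Six months of follow-up fits inside it only for women invited on the first day.

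What matters is how the data are then taken. Section 3's phrase about collation three months from the written invitations can mean each woman's own letter, or a single calendar date counted from the first batch. If two calendar pulls are made, or the data are cut at month 6, women invited late would be recorded as non-attenders while their window was still open. Some would not yet have had the reminders that are part of the intervention, because these go out 7 and 2 days before the appointment.

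Women in all three arms are randomised over the same period, so letter dates should be balanced and this would not favour an arm. It would lower measured uptake in every arm, shrink the absolute difference and cost power. The reported figure would also not be the three-month uptake that section 3.1 defines.

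**Working it through.** **Inputs from the protocol.** Study end: month 6 (summary, section 6). Follow-up: 3 and 6 months from the letter (sections 3 and 3.1). Sample size: a minimum of 2,797 per arm, 8,391 in total, for 5% type 1 error, 80% power and a 3% effect (section 7).

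**Assumptions.** Section 7 states neither the control uptake nor whether the test is one- or two-sided. I use 70% versus 73%; section 1.1 gives 70% as the acceptable coverage target and 67.3% as London coverage. I also assume letters spread evenly over A months and, for the adverse case, a data cut at month 6.

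**1. Reproducing the sample size.** With n = (z_alpha + z_beta)² × [p1(1−p1) + p2(1−p2)] / (p2−p1)²:

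- One-sided 5%: (1.645 + 0.842)² × (0.2100 + 0.1971) / 0.0009 = 2,796.6, so 2,797. This matches.
- Two-sided 5%: 3,551.

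At 70% the planned figure therefore matches a one-sided test. With 2,797 per arm, power before any truncation is 80% one-sided and 70% two-sided. I give both below. The unstated sidedness is a separate matter.

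**2. When each woman's window closes.** A letter sent in month t closes at t + 3 for the primary outcome and t + 6 for the later one. For t = 5 these are months 8 and 11. Closing by month 6 requires t ≤ 3 and t = 0 respectively.

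**3. Share with a full window at month 6.** Share = min(1, (6 − f)/A), where f is the follow-up needed. For f = 3, analysing complete cases only:

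| Letters spread over | Share with 3 months | Women per arm | Power, one-sided | Power, two-sided |
|---|---|---|---|---|
| up to 3 months | 100% | 2,797 | 80% | 70% |
| 4 months | 75% | 2,098 | 69% | 58% |
| 5 months | 60% | 1,678 | 61% | 49% |
| 6 months | 50% | 1,398 | 55% | 42% |

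Last row, two-sided: standard error = √(0.4071/1,398) = 0.01707; 0.03/0.01707 = 1.758; 1.758 − 1.960 = −0.202, which gives 42%. With 67.3% control uptake, two-sided power goes from 68% to 40%.

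For f = 6 the share is (6 − 6)/A = 0 for any rolling invitation schedule.

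**4. Keeping every woman at the cut.** Let letters run over 6 months and let attendances fall evenly over the 3 months after the letter. The first half of invitees are captured in full and the second half on average by half: 0.5 × 1 + 0.5 × 0.5 = 0.75. Uptake of 70% versus 73% then appears as 52.5% versus 54.75%, a difference of 2.25 points. Standard error = √((0.2494 + 0.2477)/2,797) = 0.01333; 0.0225/0.01333 = 1.688. Power is 39% two-sided and 52% one-sided.

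Other attendance patterns move this:

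- Attendances spread from month 1 to month 3: 67% captured, 2.0 points, 32% two-sided, 44% one-sided.
- All attendances by 1.5 months: 88% captured, 2.6 points, 53% two-sided, 65% one-sided.

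**5. No cut at month 6.** If each woman is followed from her own letter, nothing is lost. Letters over the full 6 months then need data to about month 9 for the primary outcome and month 12 for the later one.

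**The case against.** A reader might infer that later invitees cannot reach the outcome and that uptake will be truncated. The documents do not support that. It needs a hard data cut at month 6, and no section states one. Section 6 puts the uptake assessment after the six-month period, section 3.1 already anchors the outcome to the letter, and section 7 mentions a follow-up period, though only under data retention and without a length. Attendance is a routine record that the hub could extract later. Six months may have been meant as the invitation and messaging window, and section 3's wording on duration could even be read as longer than six months. This stands as far as it goes. But section 6 fixes the end without qualification, and a pull on the day after month 6 would satisfy its wording.

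A reader might also take the lack of letter and attendance dates in section 7's variable list as proof of misclassification. It is not. The list is introduced as what extraction will include, and it also omits trial arm, without which there is no analysis. The hub could apply the three-month rule before transfer, and the data-flow figure was not available to me.

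The power figures are an adverse case. Setting 42% against the planned 80% would mix a two-sided result with a one-sided plan; timing alone accounts for 70% to 42%, or 80% to 55%. The sample size is also a minimum. Randomising everyone due over 6 months could give more women per arm, and stopping at 8,391 could finish the letters sooner. A larger sample would cushion power but would not restore the three-month outcome as defined. Finally, the six-month result would be empty only if incomplete women were dropped; if kept, it is diluted.

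**Conclusion.** The contradiction in the timeline is certain on the protocol's own words: one six-month study, randomisation throughout it, and outcomes at 3 and 6 months from the letter cannot all be completed by the stated end. Only women invited at initiation could reach the six-month outcome by then.

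Truncation is conditional on how the data are pulled. For the primary outcome the effect ranges from nothing (all letters out by month 3, or extraction that waits) to half the women lacking a full window. At that adverse end, with the planned minimum per arm and the assumed uptake, power falls by roughly 25 to 31 points: 80% to 55% or 52% one-sided, 70% to 42% or 39% two-sided, depending on whether incomplete women are dropped or kept. These figures rest on even invitations and, where women are kept, even attendance over three months; neither has support in the documents. The expected harm is dilution and lost power, not bias towards an arm. The point should be corrected, because it concerns what the primary outcome measures and the remedy is cheap.

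**What to change.** - In the summary, section 3 and section 6, state the date of the last invitation letter for the study.
- Set the primary extraction at least 3 months after that letter, and the final extraction and end of study at least 6 months after it.
- In section 3.1, define uptake for each woman as attendance within 3 months, and separately within 6 months, of her own letter.
- In section 7, have the hub supply letter and attendance dates, or per-woman 3- and 6-month attendance flags if dates should not leave the service.

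This takes protocol wording and a later pull from a routine system, with no extra women or contacts. The price is time: if letters run for the full six months, primary data are complete at about month 9 and six-month data at about month 12. I would not try to save that time by sending all letters at the start, since this would alter the hub's existing invitation scheduling.

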
Don't forget your breast screening appointment is at 10:36 am on 26/10/2021 at Edgware Community Hospital. To re-arrange or cancel your appointment call [name] or visit www.london-breastscreening.org.uk For further info please click here: https://youtu.be/7CAJqKnxKa4
	
Following the breast cancer screening letter you received, don't forget your appointment is at 10:36am on 26/10/2021 at Edgware Community Hospital. Detecting breast cancer early gives you the best chance to fully recover. To find out why we're inviting you and what to expect watch this video: https://youtu.be/7CAJqKnxKa4 To re-arrange or cancel your appointment call [name]
	
Following the breast cancer screening letter you received, don't forget your appointment is at 10:36am on 26/10/2021 at Edgware Community Hospital. Detecting breast cancer early gives you the best chance to fully recover. To find out why we're inviting you and what to expect watch this video: https://imperial.ac.uk/ABBS To re-arrange or cancel your appointment call [name]

---	--	--

Message sent 7 days after the open invitation to book an appointment		
a) Control	b) Behavioural SMS	c) Behavioural SMS + Video

Breast Screening appointments have changed. You will have received a letter on how to book an appointment. Please call the London Breast Screening Hub on [name] or visit www.london-breastscreening.org.uk to arrange an appointment at your nearest location. For further info please click here: https://youtu.be/7CAJqKnxKa4"
	
Breast Screening appointments have changed. You will have received a letter on how to book an appointment. Please call the London Breast Screening Hub on [name] or visit www.london-breastscreening.org.uk to arrange an appointment locally.
 
Detecting breast cancer early gives you the best chance to fully recover. To find out why we're inviting you and what to expect watch this video: https://youtu.be/7CAJqKnxKa4
	
Breast Screening appointments have changed. You will have received a letter on how to book an appointment. Please call the London Breast Screening Hub on [name] or visit www.london-breastscreening.org.uk to arrange an appointment locally.
 
Detecting breast cancer early gives you the best chance to fully recover. To find out why we're inviting you and what to expect watch this video: https://imperial.ac.uk/ABBS

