8.2. CONSENT

No consent will be sought from participants, as the act of alerting them to differing message contents can impact upon their behaviour and may bias results. For example, alerting participants to a breast screening project using messages to improve uptake, may act as a prompt for individuals who may have not attended to attend. Furthermore, there is a need to test such messaging as a population-level intervention, to see if it has an overall effect. Basing such testing on small groups that have explicitly consented, will likely bias findings, and ignore the impact upon under-represented groups. Moreover, the current project is simply changing the wording of messages and incorporating a different video intervention, which has been approved by NHSE. Screening services have the capacity to autonomously change the content of screening reminders, for example in response to fluctuating uptake or change health policies on a local level. Explicit consent therefore is not being sought for this project, as it does not diverge from the existing care that individuals currently receive. Not requiring consent is in keeping with existing projects that have received ethical approval and been conducted in England on the use of behavioural science messaging (16,17).

On the other hand, written consent will be sought from the online feedback form for the video intervention. Participants will be free to withdraw from completing this questionnaire at any time, or not to undertake the survey at all should they wish. Consent to enter the study will be sought from each participant only after a full explanation has been given, an information leaflet offered, and time allowed for consideration. An online participant consent will be obtained. The right of the participant to refuse to participate without giving reasons will be respected.

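### Seeking feedback through the arm-c video website during the trial may give that arm alone a study-awareness prompt before the 3-month outcome is fixed

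*Combined protocol and SAP*

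**What the plan says.** Section 6 plans two rounds of feedback on the video: "At two time-points (during and at the end of the study period) feedback from participants who have watched the video will be sought". On where the form sits, it adds: "This feedback will be hosted on the video website and will be optional". The questionnaire is anonymous, asks for views on the video itself, needs informed consent, and is given as a separate survey link.

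Section 3 puts the video on a private page, "which will be available only to those who have been sent the link". Figure 1 shows who is sent it. Arm c is told to "watch this video: https://imperial.ac.uk/ABBS", and arm b to "watch this video: https://youtu.be/7CAJqKnxKa4". Arm a carries the same YouTube address as arm b.

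Section 8.2 gives the reason for not seeking consent to the trial: "alerting participants to a breast screening project using messages to improve uptake, may act as a prompt". The same section requires consent on the online feedback form and goes on: "Consent to enter the study will be sought from each participant only after a full explanation has been given, an information leaflet offered".

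Section 3.1 sets the primary outcome as uptake three months after the invitation letter, with the analysis repeated at six months.

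**The concern.** Sections 6 and 8.2 pull against each other. Section 8.2 treats knowledge of the project as something that may change attendance, and on that ground keeps it from every woman in the trial. Section 6 then makes it available, part-way through the trial, to women who open one arm's link. Nothing holds the form back until a woman's outcome is known, and nothing comparable is offered in arms a and b.

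At stake is what an arm-c result would mean. If the feedback invitation moves attendance at all, arm c tests the new video plus that invitation. A larger sample does not remove such a shift. Nor can it be adjusted for: the questionnaire is anonymous, and the variables listed for extraction in section 7 include neither page visits nor sight of the form.

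**Working it through.** **1. Can exposure come before the outcome?** Section 3 sends the link 7 days after an open invitation, before booking, and again 7 and 2 days before an appointment. All of these precede attendance. A woman who opens the arm-c link while the form is live can therefore meet the invitation first. Section 6 does not date the mid-study time-point or say how long the form stays up.

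**2. Is it confined to arm c?** Yes, apart from forwarded links. Only arm-c messages carry the new address.

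**3. Which contrasts are touched?** Within each message type in figure 1, the arm-b and arm-c texts differ only in the web address.
- c versus b isolates the exchange of the existing video for the new one. It is the contrast most compromised.
- c versus a already combines new message text with the new video. The prompt adds a further component.
- b versus a is unaffected.

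**4. The plan's own figure.** Section 7 gives 2797 per arm (3 x 2797 = 8391) for 5% type 1 error, 80% power and an effect of 3%, read here as 3 percentage points. It states neither the baseline nor the sidedness. Assuming 70% versus 73%, one-sided, unpooled:

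n = (1.6449 + 0.8416)^2 x (0.70 x 0.30 + 0.73 x 0.27) / 0.03^2 = 6.1826 x 0.4071 / 0.0009 = 2796.6, rounded up to 2797.

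The figure is reproduced under those assumptions. The present point does not depend on it, except that 3 points and 2797 serve as yardsticks below.

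**5. Illustrative size.** Intention-to-treat shift in arm c = 0.80 x s x e, where:
- 0.80 is the share of invitees with a mobile number (section 3.1);
- s is the share of messaged women who meet the form before attending (not in the documents; assumed 5% to 40%);
- e is the change in attendance it causes in them (not in the documents; assumed 1 to 10 points).

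The last column is the two-sided 5% false-positive rate for c versus b or c versus a, with 2797 per arm and uptake taken as the 67.3% London coverage in section 1.1. The standard error of a difference is sqrt(2 x 0.673 x 0.327 / 2797) = 1.25 points.

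| s | e (points) | Shift (points) | Share of 3 points | False-positive rate |
|---|---|---|---|---|
| 5% | 1 | 0.04 | 1% | 5.0% |
| 10% | 5 | 0.4 | 13% | 6.2% |
| 20% | 5 | 0.8 | 27% | 9.8% |
| 40% | 5 | 1.6 | 53% | 25% |
| 40% | 10 | 3.2 | 107% | 72% |

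The table takes the shift as positive, the direction section 8.2 has in mind. If the form puts women off, the sign reverses.

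**The case against.** The strongest reply is that few women may be exposed, and to little. Section 6 gives the questionnaire as a separate survey link, and section 8.2 attaches consent to the feedback form. A viewer may see only an optional invitation, with the explanation and leaflet a click away for those who choose to proceed. The questions concern the video, not screening behaviour. Nothing shows that the invitation reveals randomisation or the aim of raising uptake. The sentence requiring a full explanation speaks of entry to the study, which conflicts with the waiver just above it and may be template wording. Deferring the form could also cost most of the recipient feedback.

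All of this bears on size and on the cost of the remedy, and it stands to that extent. It does not remove the asymmetry: the form is offered through one arm's page, during the trial, with no safeguard.

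A reader might also infer more than the documents support:
- That section 8.2 says awareness would bias attendance. It says only that it may.
- That c versus a would otherwise measure the video alone. It would not, because the message text also changes.
- That the shift is 13% to 40% of the target effect. That follows from assuming 10% to 30% of messaged women open the page and a 5-point prompt: 0.80 x 0.10 x 5 = 0.4 points and 0.80 x 0.30 x 5 = 1.2 points, each divided by 3. The opening rate is not in the documents. The 5 points are section 1.1's figure for a reminder SMS, whereas these women have already had the SMS and opened its link. The sum also assumes that every opener meets the form before attending.

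**Conclusion.** The point holds as a design inconsistency. Sections 6 and 8.2 are not reconciled, and some arm-c women may meet a feedback invitation, and possibly a study explanation, before their primary outcome is fixed, with no counterpart in arms a and b and no record of who was exposed.

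Its size cannot be estimated from the documents. On the assumed ranges the shift runs from negligible (0.04 points, false-positive rate still about 5.0%) to 1 point or more. The upper rows of the table need both wide exposure and a strong prompt, and nothing in the protocol establishes either. The direction is uncertain. A reader should not conclude that an arm-c result will be materially biased, only that the plan leaves an avoidable rival explanation open. It is a cheap improvement of low to moderate priority.

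**What to change.** In section 6, delete the mid-study time-point. Open the questionnaire, leaflet and consent form only after the last randomised woman's 3-month primary window has closed, and amend section 8.2 to match. Deleting the mid-study time-point alone may not be enough: section 6 ends the study 6 months after initiation, so if invitations continue past month 3 (6 - 3 = 3), some primary windows would still be open at the end-of-study round.

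If mid-study feedback from recipients must be kept, show only a neutral link inviting comments on the video, with no mention of a study or of attendance. Keep the explanation and consent behind that link, and log the dates on which it is live so that a sensitivity analysis can compare periods with and without it. That analysis needs invitation or message dates, which section 7 does not list for extraction.

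The change is one of wording and of a web link's go-live date; the sample size stays at 2797 per arm. The real cost is fewer and later responses, possibly far fewer, because women reach the page mainly through messages sent before attendance. Against that, feedback on the video is not among the outcomes in section 3.1, and section 6 already plans an end-of-study round.
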